1.1 Introduction

1.1.1 Study design

This is a randomized, subject-blinded and evaluator-blinded study comparing the pain and the safety profile associated with correction of moderate to severe nasolabial folds (NLFs) using Restylane® Perlane Lidocaine (Perlane-Lido) compared to Restylane® Perlane (Perlane).

The study will be conducted at approximately 3 sites located in Taiwan and subjects aged 20 or older of Chinese origin will be enrolled. Each subject will be involved in the study for up to 31 days, including the screening period.

For more information regarding the study, please refer to the Clinical Study Protocol (CSP), MA-34273.

1.1.2 Number of subjects and randomization

The aim is to include 70 subjects treated with Perlane-Lido in one NLF and Perlane in the opposite NLF, as randomly assigned to one of the following treatment sequences:

- Perlane-Lido in the subject's right NLF followed by Perlane in the subject's left NLF.
- Perlane in the subject's right NLF followed by Perlane-Lido in the subject's left NLF.

Treatment will always start in the subject's right NLF.

1.2 Study Objectives

1.2.1 Primary objective

The primary objective is to evaluate the pain associated with injections of Perlane-Lido compared to Perlane for correction of moderate to severe NLFs.

1.2.2 Secondary objective

The secondary objective is to evaluate the dermal filler effectiveness of Perlane-Lido compared to Perlane for correction of moderate to severe NLFs.

 GALDERMA	Title SAP 43TW1628, Restylane Perlane Lidocaine vs. Restylane Perlane	Doc id MA-34458
--	---	---------------------------

1.2.3 Safety objective

The safety objective is to evaluate the safety of Perlane-Lido and Perlane throughout the study.

1.3 Pain Assessments

1.3.1 Visual Analog Scale (VAS)

The VAS is a subjective scale used to measure pain intensity (Figure 1). The subject shall be instructed to put a vertical mark (|), approximating the pain experienced during the procedure, on a 100 mm horizontal line labeled 'No pain' at the left end and 'The worst pain you can imagine' at the right end. The VAS score is obtained by measuring the distance from the left end ('No pain') to the subject's VAS mark with a standard ruler.

Figure 1: Visual Analog Scale (VAS)

No pain ————— The worst pain you can imagine

Subjects will evaluate injection site pain for each side of the face at the time of injection (before massaging) and at 15, 30, 45, and 60 minutes post-treatment by completing a VAS.

1.4 Dermal Filler Effectiveness Assessments

2017-09-07 12:43

Effective date:

Effective

Version: 1.0

A horizontal bar chart showing the distribution of 1000 samples across 10 categories. The categories are represented by vertical bars on the left, each with a black segment at the top and a white segment below. The length of the black segment corresponds to the value of the sample for that category. The categories are ordered from highest to lowest value.

Category	Value
1	980
2	950
3	900
4	850
5	800
6	750
7	700
8	650
9	600
10	550

A large black rectangular redaction box covers the majority of the page content, starting below the header and ending above the footer. It is positioned in the center of the page.

10. **What is the primary purpose of the *Journal of Clinical Endocrinology and Metabolism*?**

 GALDERMA	<small>Title</small> SAP 43TW1628, Restylane Perlane Lidocaine vs. Restylane Perlane	<small>Doc id</small> MA-34458
--	--	--

1.4.3 *Photography*

Digital photographs, taken of each subject pre-treatment at baseline, will be used [REDACTED]

1.5 Endpoints

1.5.1 *Primary endpoint*

- (i) Proportion of subjects that have a within-subject difference in VAS score (Perlane – Perlane-Lido) of at least 10 mm at injection.

1.5.2 *Secondary endpoints*

- (ii) Proportion of subjects that have a within-subject difference in VAS score (Perlane – Perlane-Lido) of at least 10 mm at 15, 30, 45, and 60 minutes after injection.

[REDACTED]

[REDACTED]

[REDACTED]

[REDACTED]

[REDACTED]

[REDACTED]

[REDACTED]

[REDACTED]

1.6 Safety Assessments

The methods for collecting the safety data are described in Section 9 of the CSP and include assessments of pre-defined, expected post-treatment events collected in the subject diary, Adverse Events (AEs), and device deficiency.

 GALDERMA	Title SAP 43TW1628, Restylane Perlane Lidocaine vs. Restylane Perlane	Doc id MA-34458
--	---	---------------------------

The subject will be instructed by the Investigator to record symptoms [REDACTED]

[REDACTED]

Each subject will be questioned about AEs at each clinical visit following the screening visit. A two-point scale ('Yes' or 'No') will be used to assess causality of AEs, serious as well as non-serious. The investigator shall be asked to indicate a response to each of the following questions in the electronic case report form (eCRF):

- *"Do you consider that there is a reasonable possibility that the event may have been caused by the study product?"* and
- *"Do you consider that there is a reasonable possibility that the event may have been caused by the study product injection procedure?"*

If any of these questions are answered with a 'Yes', the AE will be considered related.

Each AE will also be assessed for causal relationship and seriousness by the Sponsor, in order to fulfill regulatory requirements. In case of a disagreement, the AE will be considered 'Related'.

Digital photographs, taken at baseline and day 15 follow-up visit, will be used to document AEs in the treated area. If necessary, additional photo should be taken when AEs have occurred. No covering make-up should be used in the photographs.

Any device deficiencies discovered in relation to treatment at baseline and day 15 follow-up visit will be recorded.

1.7 Safety Endpoints

Safety endpoints include:

- (i) Incidence, intensity, duration and onset of related AEs collected throughout the study.
- (ii) Incidence, intensity, and number of days with pre-defined, expected post-treatment events collected using a subject diary for 14 days after treatment.

[figure not shown]
Number of days is defined as the total number of days with any observed event (to any intensity level) in a subject's diary.

 GALDERMA	<small>Title</small> SAP 43TW1628, Restylane Perlane Lidocaine vs. Restylane Perlane	<small>Doc id</small> MA-34458
--	--	--

2 Statistical Methods

2.1 General Methods

All statistical analyses, including summary tables and data listings, will be performed using the SAS® system (version 9). Confidence intervals will be two-sided and constructed at the 95% confidence level.

2.2 Analysis Populations

The following populations will be defined:

- Safety
- Full Analysis Set (FAS)
- Per Protocol (PP)

The FAS population is the primary population for all effectiveness analyses. All safety analyses will be based on the Safety population. If there are any CSP deviations considered to have substantial impact on the primary effectiveness outcome at time of injection, a PP population excluding those subjects will be defined.

2.3 Study Subjects

2.3.1 Subject disposition

The disposition of subjects (Table 4-1) will be presented by site, and in total, including number and percentage of subjects that were screened, enrolled and withdrawn.

The number of withdrawn subjects will also be accounted for by visit, as well as number of completed subjects (Figure 2).

Screening failures, if applicable, will be listed by subject screening number, and reason for screening failure (Table 4-2).

2.3.2 Analysis populations

2.3.3 Protocol deviations

Definition of protocol deviations that will exclude subjects from the PP population are defined (but not limited to) in Table 2-1 below.

Table 2-1: Protocol deviations excluding subjects from the PP population

	■	
	■	
	■	
	■	
	■	
	■	
	■	

 GALDERMA	Title SAP 43TW1628, Restylane Perlane Lidocaine vs. Restylane Perlane	Doc id MA-34458
--	---	---------------------------

2.3.4 Demographics and baseline characteristics

[REDACTED]

2.3.5 Medical history, and concomitant medication and procedures/treatments

All summaries will be based on the FAS population. Medical history will be coded according to medical dictionary for regulatory activities (MedDRA). Concomitant medications will be coded using the World Health Organization (WHO) Drug Dictionary.

Medical history/concurrent disease

[REDACTED] subjects reporting facial dermatological procedures or surgeries performed [REDACTED] will be presented.

[REDACTED] subjects reporting relevant medical history/concurrent diseases and prior facial dermatological procedures performed [REDACTED] will be summarized by [REDACTED]

[REDACTED]

Concomitant medication and procedures/treatments

[REDACTED] subjects reporting concomitant medication will be summarized in total (Table 6-1)

[REDACTED]

Concomitant medication taken due to an AE will be summarized [REDACTED]

[REDACTED]

[REDACTED]

 GALDERMA	<small>Title</small> SAP 43TW1628, Restylane Perlane Lidocaine vs. Restylane Perlane	<small>Doc id</small> MA-34458
--	--	--

2.3.6 *Extent of exposure*

[REDACTED]

[REDACTED]

[REDACTED]

2.4 Primary and Secondary Analyses

2.4.1 *Data sets analyzed*

All variables will be analyzed using the FAS population. The primary analysis will also be repeated using the PP population. If it is deemed necessary, other analyses will be repeated using the PP population.

2.4.2 *Handling of missing data*

As the study design is intra-individual, in which the outcome of both treatments to be compared is available on each subject, it is expected that when a data is missing, it will be missing for both NLFs in most of the cases. A majority of the deviations from the protocol can be expected to affect both NLFs and evaluations of the same subject the same way.

[REDACTED]

All other endpoints will be analyzed on available data, i.e. no imputations will be done.

(i) Sensitivity analysis

[REDACTED]

 GALDERMA	<small>Title</small> SAP 43TW1628, Restylane Perlane Lidocaine vs. Restylane Perlane	<small>Doc id</small> MA-34458
--	--	--

2.4.3 Primary analysis

The proportion of subjects that have a within-subject difference in VAS (Perlane minus Perlane-Lido) of at least 10 mm at the time of injection will be calculated together with a two-sided 95% confidence interval. The objective is to show that the confidence interval lies above 50% based on the FAS analysis set. To assess the robustness of the results, the same analysis will be re-run using the PP analysis set (Table 8-1).

The calculation of this proportion utilizes the split-face design of the study since it is based on within-subject difference in pain. The limit of 50% is chosen in order to show that the majority of subjects have at least 10 mm less pain when treated with Perlane-Lido as compared to Perlane.

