4.2 Number of Subjects

The study will be performed at approximately 3 hospitals in Taiwan and 70 subjects will be randomised and treated.

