2.4.4 Secondary analysis

The proportion of subjects that have a within-subject difference in VAS of at least 10 mm at post injection time points (15, 30, 45 and 60 minutes after injection) will be calculated together with a two-sided 95% confidence interval (Table 9-1). The mean VAS by treatment (Table 9-2 and Graph 9-1) and the mean within-subject difference in VAS (Table 9-3) will be calculated at each time point (at injection and 15, 30, 45 and 60 minutes after injection) and presented using descriptive statistics for continuous endpoints.

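### Does the primary analysis need a named confidence-interval method, given that at 70 subjects the choice can move the pass mark by one responder?

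*SAP*

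**What the plan says.** The primary endpoint in SAP 1.5 is a single binomial proportion: "Proportion of subjects that have a within-subject difference in VAS score (Perlane – Perlane-Lido) of at least 10 mm at injection". SAP 2.4.3 states that this proportion "will be calculated together with a two-sided 95% confidence interval. The objective is to show that the confidence interval lies above 50" per cent in the full analysis set (FAS). The threshold is explained in the same section: "The limit of 50% is chosen in order to show that the majority of subjects have at least 10 mm less pain". The general rule in SAP 2.1 adds only level and sidedness: "Confidence intervals will be two-sided and constructed at the 95% confidence level".

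For the per-protocol (PP) set, SAP 2.4.3 says that "the same analysis will be re-run using the PP analysis set (Table 8-1"), as a check of robustness. For the later time points, SAP 2.4.4 says that each proportion "will be calculated together with a two-sided 95% confidence interval (Table 9-1"), with no threshold attached.

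On numbers, SAP 1.1.2 states that "The aim is to include 70 subjects treated with Perlane-Lido in one NLF and Perlane in the opposite NLF", and protocol 4.2 that "70 subjects will be randomised and treated". Protocol 11.5 sets a missing difference at injection to 0 mm in the FAS.

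No readable section names Wald, Wilson, Clopper-Pearson or any other interval. The following cannot be read: the statistical methods in the protocol synopsis; protocol 11.1, 11.4 and the sample-size section; and SAP 2.7, 2.8 and Appendix A5, which holds the shell for the primary table.

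**The concern.** In the readable text the lower confidence limit is the only success rule for the primary endpoint. With a discrete count and a fixed threshold, the interval method sets the smallest number of responders that counts as success. If the method is open, two analysts could read the same data set differently, one reporting that the primary objective was met and the other that it was missed. The choice could also be made after the count is known.

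Error control is involved as well. A two-sided 95% interval suggests 2.5% error in the upper tail, although the readable text states only the confidence level. Approximate intervals do not hold 2.5% at every sample size, so an open method also leaves the false-positive rate open.

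**Working it through.** **Inputs.** n = 70 (SAP 1.1.2, protocol 4.2); two-sided 95%, so z = 1.959964 (SAP 2.1, 2.4.3); success if the lower limit exceeds 0.50 (SAP 2.4.3). The readable documents give no pass mark, expected response rate or power, so there is no plan figure to reproduce. The true rates used below are assumptions.

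**Wald.** Lower limit = p − z·√(p(1 − p)/n).
- 43/70: p = 0.61429; √(0.61429 × 0.38571/70) = 0.05818; lower limit = 0.61429 − 0.11403 = 0.50026. Pass, narrowly.
- 42/70: lower limit 0.48524. Fail.

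**Wilson.** The lower limit exceeds 0.50 when (x − n/2)/√(n/4) > z. Here n/2 = 35 and √17.5 = 4.1833.
- 43: 8/4.1833 = 1.912. Fail (lower limit 0.4972).
- 44: 9/4.1833 = 2.151. Pass (lower limit 0.5115).

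**Clopper-Pearson.** The lower limit exceeds 0.50 when P(X ≥ x | n, 0.5) < 0.025.
- 43: P = 0.0361. Fail (lower limit 0.4903).
- 44: P = 0.0207. Pass (lower limit 0.5048).

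Agresti-Coull, Jeffreys, mid-P and the continuity-corrected forms of Wald and Wilson also need 44. Wald is the only one of the eight methods tried that passes at 43.

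**Chance that the method matters at n = 70.** This is P(X = 43), which is also the difference in power between a cut of 43 and a cut of 44.

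| Assumed true rate | P(X ≥ 43) | P(X ≥ 44) | P(X = 43) |
|---|---|---|---|
| 50% | 3.61% | 2.07% | 1.5% |
| 60% | 45.5% | 36.0% | 9.5% |
| 65% | 77.5% | 69.5% | 8.0% |
| 70% | 95.2% | 92.2% | 3.0% |
| 75% | 99.6% | 99.2% | 0.4% |

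At 80% the chance of exactly 43 is 0.02%.

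**Other sizes.** Smallest passing count, with its one-sided error at a true rate of 50%:

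| n | Wald | Wilson | Clopper-Pearson |
|---|---|---|---|
| 66 | 41 (3.20%) | 41 (3.20%) | 42 (1.78%) |
| 67 | 42 (2.49%) | 42 (2.49%) | 42 (2.49%) |
| 68 | 42 (3.41%) | 43 (1.92%) | 43 (1.92%) |
| 69 | 43 (2.66%) | 43 (2.66%) | 44 (1.47%) |
| 70 | 43 (3.61%) | 44 (2.07%) | 44 (2.07%) |

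Over n = 60 to 70, Wald passes one responder earlier than Clopper-Pearson at 8 of 11 sizes and Wilson does so at 5 of 11. The gap is never more than one. At those sizes their error exceeds 2.5%, with maxima of 3.61% for Wald and 3.20% for Wilson. The Clopper-Pearson maximum is 2.49%.

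**Where the other sizes apply.** Pain at injection is scored during the Day 1 treatment visit, so later dropout does not remove it. The 0 mm rule turns a missing score into a non-responder and keeps the subject in the denominator. If the FAS is all treated subjects (its definition is not readable), the primary analysis stays at the number treated. The smaller sizes then concern mainly the PP re-run, which carries no success rule.

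**The case for a change.** The strongest case for a change is that SAP 2.4.3 and 2.1 are the natural places to name the method and neither shows a gap where it might have been blacked out. The interval is the decision rule, one sentence would settle it, and Clopper-Pearson holds one-sided error at or below 2.5% at every size, whereas Wald and Wilson do not. Because 70 is an aim, the match between Wilson and Clopper-Pearson at 70 is partly luck: at 69 they differ by one responder.

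Much of this stands. The arithmetic is right, naming an interval in advance is good practice, and Wald is the weakest of the three choices at 70.

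It does not show that the plan lacks a method. A plan can name the interval once, in the protocol's analysis or sample-size section or in the table shell, and those are the parts that cannot be read. The case for Clopper-Pearson over Wilson rests on strict 2.5% control, which the readable text does not require, and at 70 the two give the same cut and the same error. An interval imposed from outside could also disagree with the one used for the unreadable sample-size calculation. For the proportions in SAP 2.4.4 there is no threshold, so the method would change only the printed limits.

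**Conclusion.** No change to the plan is called for. The readable text leaves the interval type unstated, but whether the plan as a whole does so cannot be determined. If it does, this is missing detail that an analyst fills with a standard interval, and no stated rule produces a wrong result.

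At a FAS of 70 the exposure is a single count: exactly 43 responders, analysed by Wald. The cost of that choice would be a one-sided error of 3.61% in place of 2.07% at a true rate of 50%. The chance of meeting that count is 3.0% or less at the true rates of 70% and above shown here, and reaches 8.0 to 9.5% only at 60 to 65%, where either cut has power below 78%.

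This rests on three assumptions: that the FAS stays at or close to 70, that the true rates used here span the plausible range (no expected rate is readable), and that 2.5% per tail is the relevant benchmark. If the FAS falls slightly short of 70, the methods still differ by at most one responder over the sizes checked (60 to 70).

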2.4.4 Secondary analysis

The proportion of subjects that have a within-subject difference in VAS of at least 10 mm at post injection time points (15, 30, 45 and 60 minutes after injection) will be calculated together with a two-sided 95% confidence interval (Table 9-1). The mean VAS by treatment (Table 9-2 and Graph 9-1) and the mean within-subject difference in VAS (Table 9-3) will be calculated at each time point (at injection and 15, 30, 45 and 60 minutes after injection) and presented using descriptive statistics for continuous endpoints.

2.5 Safety Analysis

All safety variables will be summarized descriptively based on the safety population.

2.5.1 Predefined, expected post-treatment events

 GALDERMA	<small>Title</small> SAP 43TW1628, Restylane Perlane Lidocaine vs. Restylane Perlane	<small>Doc id</small> MA-34458
---	--	--

[figure not shown]
2017-09-07 12:43

Effective date:

Effective

2.5.2 *Adverse events*

[figure not shown]
[figure not shown]
All AEs will be summarized and listed by SOC and PT assigned using MedDRA.

All AEs will be included in the data listings. Any serious Adverse Events and/or AEs that led to withdrawal will be listed separately.

2.6 **Interim Analysis**

No interim analysis is planned.

Version: 1.0

 GALDERMA	<small>Title</small> SAP 43TW1628, Restylane Perlane Lidocaine vs. Restylane Perlane	<small>Doc id</small> MA-34458
---	--	--

Effective date:

Effective

Version: 1.0

[REDACTED] [REDACTED]

[REDACTED]

[REDACTED]	[REDACTED]	[REDACTED]	[REDACTED]	[REDACTED]
[REDACTED]	[REDACTED]	[REDACTED]	[REDACTED]	[REDACTED]
[REDACTED]	[REDACTED]	[REDACTED]	[REDACTED]	[REDACTED]
[REDACTED]	[REDACTED]	[REDACTED]	[REDACTED]	[REDACTED]
[REDACTED]	[REDACTED]	[REDACTED]	[REDACTED]	[REDACTED]

2017-09-07 12:43

Effective date:

Effective

Version: 1.0

A 10x10 grid of black bars. The first two columns are solid black. The third column has a black bar at row 1 and a shorter black bar at row 2. The fourth column has a black bar at row 1 and a shorter black bar at row 3. The fifth column has a black bar at row 1 and a shorter black bar at row 4. The sixth column has a black bar at row 1 and a shorter black bar at row 5. The seventh column has a black bar at row 1 and a shorter black bar at row 6. The eighth column has a black bar at row 1 and a shorter black bar at row 7. The ninth column has a black bar at row 1 and a shorter black bar at row 8. The tenth column has a black bar at row 1 and a shorter black bar at row 9. The bottom row has a solid black bar from column 1 to column 2, and a solid black bar from column 9 to column 10.

2017-09-07 12:43

Effective date:

Effective

Version: 1.0

2017-09-07 12:43

Effective date:

Effective

Version: 1.0

10 Appendix A7: Safety Evaluation

© 2019 Pearson Education, Inc.

A 10x10 grid of black and white squares. The first two columns are black. Columns 3-4 are white. Columns 5-6 are black. Columns 7-8 are white. Columns 9-10 are black. The last row is solid black.

[REDACTED]

Title

SAP 43TW1628, Restylane Perlane Lidocaine vs. Restylane Perlane

Doc id

MA-34458

2017-09-07 12:43

Effective date:

Effective

Version: 1.0

2017-09-07 12:43

Effective date:

Effective

Version: 1.0

10 of 10

[REDACTED]

A horizontal bar chart with 10 bars. The first 9 bars are black and of varying lengths, decreasing from left to right. The 10th bar is light purple and is the same length as the 8th bar. The bars are set against a grid of light gray lines.

Title

SAP 43TW1628, Restylane Perlane Lidocaine vs. Restylane Perlane

Doc id

MA-34458

[REDACTED]

[REDACTED]

[REDACTED]

[REDACTED]								
	[REDACTED]							
	[REDACTED]							
[REDACTED]								
[REDACTED]								
[REDACTED]								
[REDACTED]								
[REDACTED]								
[REDACTED]								

[REDACTED]

